7.4 Evaluation of Overall Response

The primary endpoint of this study is best Overall Response Rate (ORR) that is determined from the start of treatment until 6 months later (Table 2). Best ORR will depend on the status of both target and non-target disease as well as whether new lesions appear. Furthermore, it is defined as the best response at all time points. When SD is the best response it must also meet protocol specified minimum time from baseline of 8 weeks. If the minimum time is not met when SD is the best time point response, then the subject's best response depends on the subsequent assessments. For example, if SD is the best response at first assessment, and has PD at the second assessment but does not meet the minimum duration of SD will have best response of PD.

Target Lesions	Non-Target Lesions	New Lesions	Overall Response
CR	CR	No	CR
CR	PR/SD	No	PR
PR	Non-PD	No	PR
SD	Non-PD	No	SD
PD	Any	Yes or No	PD
Any	PD	Yes or No	PD
Any	Any	Yes	PD

Table 3. Best Overall Response Criteria

7.5 Verification Scans

Confirmation of CR or PR is required (Table 3). Confirmed CR or PR will be claimed only if the criteria for each are met at a subsequent time point (minimum 4 weeks after criteria for an objective response are first met).

Confirmation of PD is required if PD is equivocal. If repeat scan confirms PD, then PD will be claimed using the date of the initial scan. If repeat scan does not confirm PD, then PD will not be claimed.

Overall Response At First Time Point	Overall Response At Second Time Point	Best Overall Response
CR	CR	CR
CR	PR	SD, PD, OR PR*
CR	SD	SD provided minimum criteria for SD duration met, otherwise, PD
CR	PD	SD provided minimum criteria for SD duration met, otherwise, PD
CR	NE	SD provided minimum criteria for SD duration met, otherwise, NE
PR	CR	PR
PR	PR	PR
PR	SD	SD
PR	PD	SD provided minimum criteria for SD duration met, otherwise, PD
PR	NE	SD provided minimum criteria for SD duration met, otherwise, NE
NE	NE	NE

Table 4. Best Overall Response When Confirmation of CR and PR is Required.

CR = complete response, PR = partial response, SD = stable disease, PD = progressive disease, NE= not evaluable.

*If CR is achieved at first time point, but any disease including PR at subsequent time point will result in PD. Best response would depend on whether minimum duration for SD was met. Sometimes CR may be claimed when subsequent scan suggests small lesions were likely still present and the patient had PR, not CR at first time point. If this is the case, then the original CR should be changed to PR and the best response is PR.

7.6 Evaluation of Immune-Related Overall Response

Systematic criteria designated immune-related response criteria were defined based on four distinct response patterns seen after administration of an ICI: (a) shrinkage in baseline lesions,

without new lesions; (b) durable stable disease (in some patients followed by a slow, steady decline in total tumor burden); (c) response after an increase in total tumor burden; and (d) response in the presence of new lesions. These four patterns were associated with favorable survival (30).

One secondary objective of this study is objective response rate by immune-related response criteria (irRC). Immune-related objective response rate (irORR) will be determined as published by Wolchok et al(36). irORR is the proportion of patients with best overall response of irCR or irPR from the start of the study until 6 months later. Response is defined as irCR, irPR, or irSD over at least 4 weeks.

Anti-tumor response is based on total measurable tumor burden, which is determined as follows. Only index and measurable new lesions are taken into account. At baseline tumor assessment, the sum of the products of the 2 largest perpendicular diameters (SPD) of all index lesions (5 lesions per organ, up to 10 visceral lesions and 5 cutaneous index lesions) is calculated. At each subsequent tumor assessment, the SPD of the index lesions and of new measurable lesions (at least 5 x 5 mm; up to 5 new lesions per organ: 5 new cutaneous and 10 visceral lesions) are added together to provide the total tumor burden.

Percentage changes in tumor burden per assessment time point describe the size and growth kinetics of both conventional and new measurable lesions as they appear. At each tumor assessment the response in index and new measurable lesions is defined based on the change in tumor burden (after ruling out irPD). Decreases in tumor burden must be assessed relative to baseline measurements (i.e. the SPD of all index lesions at screening).

irCR	Disappearance of all lesions in 2 consecutive observations not less than 4			
	weeks apart.			
irPR	At least 50% decrease in tumor burden compared with baseline in 2			
	observations at least 4 weeks apart.			
irSD	Neither 50% decrease in tumor burden compared with baseline cannot be			
	established nor 25% increase compared with nadir (at any time point).			
irPD	At least 25% increase in tumor burden compared with nadir (at any time			
	point) in 2 consecutive observations at least 4 weeks apart.			

Table 5. Immune-related response criteria.

Major differences with other tumor response criteria include: PR or SD in the presence of new lesions, as long as they met the respective threshold of response based on total differences in tumor burden; an SD does not require confirmation; however PD requires confirmation by another scan at least 4 weeks apart in the absence of rapid clinical deterioration.

8. SAFETY ASSESSMENT

8.1 Adverse Event Assessment

Adverse events (AEs) will be defined using the Common Terminology Criteria for Adverse Events (CTCAE) v5.0 criteria.

A causal relationship between radiation therapy/immune checkpoint inhibitor and the AE should be determined for all AEs as follows:

- Related: There is a reasonable causal relationship between radiation therapy/immune checkpoint inhibitor and the AE
- Not related: There is not a reasonable causal relationship between radiation therapy/immune checkpoint inhibitor and the AE

8.2 Definition of Adverse Event

An AE is defined as any untoward medical occurrence in a patient or clinical investigation subject administered a pharmaceutical product and which does not necessarily have a causal relationship with this treatment. An AE can therefore be any unfavorable and unintended sign (including an abnormal laboratory finding), symptom, or disease temporally associated with the use of a medicinal product, whether or not considered related to the medicinal product.

An AE includes but is not limited to any clinically significant worsening of a subject's pre-existing condition. An abnormal laboratory finding (including ECG finding) that requires an action or intervention by the investigator, or a finding judged by the investigator to represent a change beyond the range of normal physiologic fluctuation, should be reported as an AE.

Adverse events may be treatment emergent (ie, occurring after initial receipt of investigational product) or non-treatment emergent. A non-treatment emergent AE is any new sign or symptom, disease, or other untoward medical event that begins after written informed consent has been obtained but before the subject has received investigational product.

Elective treatment or surgery or preplanned treatment or surgery (that was scheduled prior to the subject being enrolled into the study) for a documented pre-existing condition that did not worsen from baseline is not considered an AE (serious or non-serious). An untoward medical event occurring during the prescheduled elective procedure or routinely scheduled treatment should be recorded as an AE or SAE.

The term AE is used to include both serious and non-serious AEs.

8.3 Serious Adverse Event Reporting

A serious adverse event (SAE) is an AE occurring during any study phase (i.e., screening, runin, treatment, wash-out, follow-up), at any dose of the study drugs that fulfills one or more of the following criteria:

- Results in death
- Is immediately life-threatening
- Requires in-patient hospitalization or prolongation of existing hospitalization
- Is a congenital abnormality or birth defect in offspring of the subject
- Is an important medical event that may jeopardize the patient or may require medical intervention to prevent one of the outcomes listed above

It is important to note that hospital admission for a planned procedure or disease treatment is not considered a SAE.

SAE reporting is required once the participant signs consent and is registered on the study.

SAE reporting is required for 30 days after the participant's last treatment administration on study. Any events that occur after this 30 day period that may be related to study treatment must be reported.

An SAE is required to be reported to the IRB within 5 calendar days of the event occurrence. A Clinical Research Database (CRDB) SAE report should be submitted to the SAE Office including the following:

- Subject's name (use initials only if the report will be sent outside of MCI)
- Medical record number
- Disease/histology
- Protocol number and title
- Date of the AE occurrence
- Describe the nature of the AE (i.e. dermatitis)
- The grade of the AE
- Relationship of the AE to treatment
- Whether the AE was expected or unexpected
- The AE severity
- The intervention to address the AE
- A description of the subject's condition
- Indication if the subject remains on the study
- If an amendment will need to be made to the protocol and/or consent form

The PI's signature and date are required on this report.

8.4 Non-Serious Adverse Event Reporting

Non-serious AE reporting will begin upon initiation of treatment and for a minimum of 100 days after completion of radiation therapy.

Non-serious AEs should be followed until resolution of stabilization.

All identified non-serious AEs must be recorded and described on the non-serious AE page of the CRF.

8.5 Immune checkpoint inhibitor toxicity management

The safety profile of immune checkpoint inhibitors given as monotherapy has been well established. Management of immune related adverse events (irAEs) should be done according to standard guidelines and includes dose adjustment or delay according to the treating medical oncologist.

Management algorithms have been developed to assess and manage the following groups of irAEs:

- Pulmonary
- Renal
- Gastrointestinal
- Hepatic
- Endocrine
- Skin
- Neurological

Hepatic Adverse Event Management Algorithm

Patients on IV steroids may be switched to an equivalent dose of oral corticosteroids (e.g. prednisone) at start of tapering or earlier, once sustained clinical improvement is observed. Lower bioavailability of oral corticosteroids should be taken into account when switching to the equivalent dose of oral corticosteroids. *I-O therapy may be delayed rather than discontinued if AST/ALT = 8 x ULN and T,bill = 5 x ULN.

**The recommended starting dose for grade 4 hepatitis is 2 mg/kg/day methylprednisolone IV.

Patients on IV steroids may be switched to an equivalent dose of oral corticosteroids (e.g. prednisone) at start of tapering or earlier, once sustained clinical improvement is observed. Lower bioavailability of oral corticosteroids should be taken into account when switching to the equivalent dose of oral corticosteroids.

Patients on IV steroids may be switched to an equivalent dose of oral corticosteroids (e.g. prednisone) at start of tapering or earlier, once sustained clinical improvement is observed. Lower bioavailability of oral corticosteroids should be taken into account when switching to the equivalent dose of oral corticosteroids.

Patients on IV steroids may be switched to an equivalent dose of oral conticosteroids (e.g. prednisone) at start of tapering or earlier, once sustained clinical improvement is observed. Lower bioavailability of oral corticosteroids should be taken into account when switching to the equivalent dose of oral corticosteroids.

Patients on IV steroids may be switched to an equivalent dose of oral corticosteroids (e.g. prednisone) at start of tapering or earlier, once sustained clinical improvement is observed. Lower bioavailability of oral corticosteroids should be taken into account when switching to the equivalent dose of oral corticosteroids.

Skin Adverse Event Management Algorithm

improvement is observed. Lower bioavailability of oral corticosteroids should be taken into account when switching to the equivalent dose of oral corticosteroids.

Neurological Adverse Event Management Algorithm

Patients on IV steroids may be switched to an equivalent dose of oral corticosteroids (e.g. prednisone) at start of tapering or earlier, once sustained clinical improvement is observed. Lower bioavailability of oral corticosteroids should be taken into account when switching to the equivalent dose of oral corticosteroids.

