8.6 Criteria to Resume Treatment

Subjects may resume receiving an immune checkpoint inhibitor when drug-related AEs resolved to no greater than Grade 1.

There are some exceptions to this, however. Subjects may resume treatment with an immune checkpoint inhibitor in the following situations:

- Grade 2 fatigue is present
- No greater than Grade 2 skin toxicity is present
- Subjects with baseline Grade 1 AST/ALT or total bilirubin who require dose delays for reasons other than a 2-grade shift in AST/ALT or total bilirubin may resume treatment in the presence of Grade 2 AST/ALT or total bilirubin
- Subjects with combined Grade 2 AST/ALT and total bilirubin values meeting discontinuation parameters should have treatment permanently discontinued.
- Drug-related pulmonary toxicity, diarrhea, colitis, must have resolved to baseline before treatment is resumed.
- Drug-related endocrinopathies adequately controlled with only physiologic hormone replacement may resume treatment.

Subjects should resume treatment at the next scheduled time point per the study protocol if criteria to resume treatment are met. If the treatment is delayed past the next scheduled time point per the study protocol, then the next scheduled time point will be delayed until dosing resumes.

Treatment may be delayed for up to 6 weeks from the last dose. If treatment is delayed by more than 6 weeks the subject will be discontinued from study therapy, except as specified.

8.7 Management of radiation therapy adverse events

Radiation therapy given as monotherapy may cause AEs specific to the location in the body being treated. For example, AEs as a result of liver treatment will be distinct from treatment of a lung lesion. Supportive care is given based on the specific AE when radiation therapy is given as monotherapy, and the same should be done when radiation is given with concurrent immune checkpoint inhibitor.

8.8 Pregnancy

If it becomes known that a subject is pregnant or may have been pregnant at the time of study participation, the investigator must immediately notify the PI ([name] at [contact]) and the Baptist Health South Florida Institutional Review Board (BHSF-IRB at [contact]) and the patient will be discontinued from study participation.

Overdose or Misadministration of Radiation

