9. SUBJECT DISCONTINUATION AND REPLACEMENT

9.1 Subject Discontinuation

Permanent withdrawal of a subject from the study will occur when any of the following occur pertaining to the subject in question:

- Subject withdraws consent or is lost to follow-up.
- Patient becomes pregnant or has the intent to become pregnant.
- Subject is non-compliant with requirements of this study (i.e. refusal to adhere to scheduled visits) that in the opinion of the investigator warrants study withdrawal.
- Confirmation of progressive disease and determination by the investigator that the subject is not receiving benefit from study therapy.
- Subject starts anti-cancer therapy with any agent not specifically included within this study's protocol.
- AE occurs that in the opinion of the investigator is a contraindication to further treatment on study.
- Any Grade 2 drug-related uveitis or eye pain or blurred vision that doesn't respond to topic therapy and doesn't improve to Grade 1 severity within the re-treatment period or requires systemic therapy.
- Grade 3 drug-related uveitis, pneumonitis, bronchospasm, neurologic toxicity, hypersensitivity reaction, or infusion reaction of any duration
- Grade 3 drug-related thrombocytopenia lasting >7 days or is associated with bleeding
- Drug-related liver dysfunction that meets the following criteria
 - a. AST or ALT >8x ULN
 - b. Total bilirubin >5x ULN
 - c. Concurrent AST or ALT >3x ULN and total bilirubin >2x ULN

- Any Grade 4 drug-related AE or laboratory abnormality with the exception of the following:
 - Grade 4 electrolyte imbalance not clinically significant and corrected with appropriate medical management within 72 hours of onset
- Any dosing delays lasting >6 weeks with the following exceptions:
 - Dosing delays to allow for prolonged steroid taper to manage drug-related AE. Tumor assessments should continue as per protocol despite dosing delay.
 - Dosing delays >6 weeks for non-drug-related reasons if approved by the primary investigator. Tumor assessments should continue as per protocol despite dosing delay.

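### The hepatic footnote in section 8.5 permits ICI delay at combined liver values for which section 9.1 requires permanent withdrawal

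*Combined protocol and SAP*

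**What the plan says.** Three sections of the protocol deal with raised liver values on the immune checkpoint inhibitor (ICI).

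- **Section 8.5**, footnote to the hepatic algorithm: "I-O therapy may be delayed rather than discontinued if AST/ALT = 8 x ULN", and the same sentence adds a total bilirubin of 5 x ULN. This is a joint condition on transaminases and bilirubin, and it grants an option.
- **Section 9.1**, opening sentence: "Permanent withdrawal of a subject from the study will occur when any of the following occur pertaining to the subject in question". One listed event is "Drug-related liver dysfunction that meets the following criteria", followed by (a) "AST or ALT >8x ULN", (b) "Total bilirubin >5x ULN" and (c) "Concurrent AST or ALT >3x ULN and total bilirubin >2x ULN".
- **Section 8.6**, among the exceptions to the rule for resuming treatment: "Subjects with combined Grade 2 AST/ALT and total bilirubin values meeting discontinuation parameters should have treatment permanently discontinued". It gives no multiples of ULN and does not say where its parameters are found.

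None of the three sections refers to another on this point or says which prevails. The exceptions written into 9.1 concern electrolyte imbalance and long dosing delays, not liver values.

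**The concern.** Criterion (c) in 9.1 concerns transaminases and bilirubin raised together, and so does the condition in the 8.5 footnote. Yet 8.5 offers a delay at values well above both thresholds in (c). A treating oncologist working from the toxicity algorithm could hold the ICI and later resume it in a patient whom 9.1 says must be withdrawn permanently.

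The situation is a plausible one in this population. Section 4.1 admits patients with liver metastases at AST/ALT up to 5 x ULN, so a patient can enter already above the transaminase part of (c). Entry bilirubin is capped at 1.5 x ULN, so nobody should meet (c) at enrolment. A later drug-related rise in bilirubin above 2 x ULN would be enough to do so.

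At stake is the consistent handling of combined liver injury, and with it the record of ICI exposure, withdrawals and treatment-related adverse events, the last of which is a secondary endpoint.

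**Working it through.** There is no sample size, power or error rate to reproduce. The check is whether the two sets of liver values overlap.

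**Notation.** A is the higher of AST and ALT, and B is total bilirubin, both in multiples of ULN.

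**Inputs.**
- 8.5, delay permitted: A = 8 and B = 5 as printed. The sign may be a misread at-most sign, giving A ≤ 8 and B ≤ 5.
- 9.1, withdrawal required if any holds: (a) A > 8; (b) B > 5; (c) A > 3 and B > 2.

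**Literal reading.** Put A = 8 and B = 5 into 9.1. (a) 8 > 8 is false. (b) 5 > 5 is false. (c) 8 > 3 and 5 > 2 are both true. Delay is permitted and withdrawal is required.

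**At-most reading.** Criteria (a) and (b) start exactly where the 8.5 range ends, so they add no overlap. The overlap comes from (c) alone: 3 < A ≤ 8 with 2 < B ≤ 5. The rest of the 8.5 range, where A ≤ 3 or B ≤ 2, is free of conflict.

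| A | B | 8.5 (at most) | 9.1 | Conflict |
|---|---|---|---|---|
| 8 | 5 | delay permitted | withdraw, by (c) | yes |
| 6 | 3 | delay permitted | withdraw, by (c) | yes |
| 3.1 | 2.1 | delay permitted | withdraw, by (c) | yes |
| 6 | 1.5 | delay permitted | no criterion met | no |
| 2.5 | 4 | delay permitted | no criterion met | no |
| 8 | 2 | delay permitted | no criterion met | no |
| 3 | 5 | delay permitted | no criterion met | no |

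**Other readings of the sign.** Strictly below gives the same overlap without its upper edges (3 < A < 8 with 2 < B < 5). Above (A > 8 and B > 5) would meet (a), (b) and (c) together. That reading would allow delay with no upper limit and nothing in the text favours it, so the point does not rely on it. No reading of the sign removes the conflict.

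**Could (a), (b) and (c) all be required together?** If A > 8 and B > 5, then A > 3 and B > 2 follow automatically, so (c) would do no work. The three are therefore alternatives.

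**Does 8.6 settle it?** It points towards permanent discontinuation for combined Grade 2 values that meet some discontinuation criteria. It neither states those criteria nor mentions the 8.5 footnote. The protocol does not translate grades into multiples of ULN, so 8.6 cannot be placed on the A and B scale from the documents alone.

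**The case against.** The strongest case on the other side has five parts.

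- **Permission against obligation.** The footnote only allows a delay, while 9.1 requires withdrawal. An investigator who withdraws the patient complies with both. This stands, and it rules out a reading that a reader might be tempted to infer: that the two sections order opposite actions. They do not. What remains is that 8.5 offers an option whose use breaches 9.1 at some values.
- **General limits plus an added rule.** The 8.5 figures of 8 and 5 match 9.1(a) and (b), so 8.5 may be stating the single-marker limits, with (c) meant to apply on top. That is a plausible account of how the text arose, but nothing in 8.5 tells its reader that (c) applies.
- **The algorithm figure is not shown.** The footnote belongs to a figure that is missing from the text available here, so the box carrying its asterisk cannot be seen. The figure might carry its own instruction for combined elevation. This is a real limit on the point and is not a fault of the plan. The footnote does state its own numeric condition, and no surviving text narrows it.
- **Different subjects.** 8.5 governs dosing and 9.1 governs withdrawal from the study. But a permanently withdrawn patient cannot merely be delayed on study ICI, and the 9.1 list itself contains drug-toxicity and dosing-delay rules.
- **Limited consequences.** The 9.1 liver rule covers drug-related dysfunction only; section 8.7 deals separately with radiation toxicity. Section 9.1 also keeps most discontinued patients in follow-up for safety, imaging and survival. This stands and limits the loss of data.

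**Conclusion.** The two safety rules are inconsistent as written. Read literally, the conflict is the single combination of 8 x and 5 x ULN. Read as at most, it is AST/ALT above 3 and up to 8 x ULN with bilirubin above 2 and up to 5 x ULN. In both cases it runs only through criterion (c) of 9.1.

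The conclusion assumes that the liver dysfunction is drug-related, that (a) to (c) are alternatives, and that the unseen algorithm figure does not already exclude the combined case. The comparison sign could not be verified. It changes the size of the overlap but not its existence.

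Three stronger inferences are not supported. The conflict does not extend across the whole 8.5 range. Section 8.6 is not a second statement of 9.1(c), because it gives no thresholds and defers to criteria it does not name. And no effect on the primary endpoint or on the Simon two-stage design has been shown. The number of patients affected cannot be derived from the documents. The point deserves correction because it concerns a safety rule and is cheap to repair.

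**What to change.** Reconcile the 8.5 hepatic footnote, 8.6 and 9.1 so that each combination of AST/ALT and total bilirubin leads to one instruction. State that instruction in one place and have the other sections refer to it. In the same edit:

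- confirm the comparison signs in the footnote against the source figure;
- say which discontinuation criteria 8.6 means;
- say which section prevails if the figure and the text differ.

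Which rule applies at which values is for the clinical team, and this review takes no view on it. The cost is protocol wording in the next amendment, with no change to sample size, visit schedule or analysis.
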